Biochemical assays: Blood levels of 25(OH)D and EPA+DHA will be assayed on participants who provide an analyzable sample at baseline and all participants who provide a blood sample at follow-up. In addition, baseline and follow-up blood levels of calcium, PTH and lipoproteins will be assayed. These assays will be performed by Quest Diagnostics. Quest Diagnostics will also perform albumin, creatinine, liver function and lipid tests on a subset of participants. In addition, we will measure several biomarkers related to CVD (including cholesterol lipoprotein subfractions using the Vertical Auto Profile cholesterol test, apolipoproteins, thyroid function, vitamin D, albumin, creatinine, PCSK9 and a basic metabolic panel). These additional

measurements will be done at Atherotec Diagnostics Lab in Birmingham, AL, which will fund the costs of these studies. In addition, PCSK (plasma-based genotype) will be assayed on participants who additionally gave genetic consent.

We will also measure metabolomic and lipidomic biomarkers on baseline and follow-up stored samples. Samples will be sent in a de-identified manner and measurements will be done at [name] laboratory at the University of California San Diego, and at LabCorp, Inc., Raleigh, NC. In a small subset of participants, we will also 1) measure cholesterol efflux and epigenetic biomarkers on participants who gave genetic consent by sending de-identified samples to our academic collaborators in Quebec, [name] and [name] (Institut universitaire de cardiologie et de pneumologie de Québec); and 2) measure additional vitamin D biomarkers on de-identified samples sent to our academic collaborators at Massachusetts General Hospital, [name] and [name].

Over 5 years of follow-up, we would expect to accrue approximately 1660 cancer cases and 990 CVD cases, with somewhat smaller numbers if the agents are highly effective. If 60% of participants provide blood specimens, this would include about 996 cancer cases and 594 CVD cases with bloods.

B. ASSESSMENT OF DIETARY AND SUPPLEMENTAL INTAKE

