A. SAFETY MONITORING

An independent Data and Safety Monitoring Board (DSMB) will be assembled, consisting of experts in clinical trials, epidemiology, biostatistics, relevant clinical areas of cancer and CVD, and NIH representatives. The Physicians' Health Study, the Women's Health Study, and the Women's Antioxidant and Folic Acid Cardiovascular Study have been monitored by the same DSMB since their inception. As two of these trials have ended and the third is in its last years, we have asked our DSMB members if they would be willing to also monitor VITAL. Four have accepted the invitation, and three new members have been added. The full 7-member DSMB has been approved by the NCI.

The DSMB will annually examine the progress of the trial and the unblinded data on study endpoints and possible adverse effects to recommend continuation, alteration of study design, or early termination, as appropriate. Interim trial results will be assessed with the Haybittle-Peto rule,^{82,83} adjusting for multiple looks. In this method, interim results are compared to a z-score of 3 standard deviations ($p=0.0027$) throughout the trial. The final results may then be interpreted as having close to nominal significance levels. This rule appropriately requires very strong evidence for early stopping, is more conservative than the Pocock⁸⁴ and O'Brien-Fleming⁸⁵ rules and the alpha-spending function,⁸⁶ and can be conducted at convenient times without inducing statistical complexity.⁸⁷

While these rules are intended for the primary endpoints, the goal of VITAL is to assess the overall balance of benefits and risks of the two agents in the primary prevention of cancer and CVD. Thus, consideration will also be given to the secondary endpoints that are needed in the interpretation of overall results. In addition, the monitoring rules will serve solely as guidelines in decisions regarding continuation or stopping of treatment arms. All decisions must be made after examining the totality of evidence, including other trial data, on these agents.

B. MONITORING OF SOURCE DATA AND DRUG DISPENSEMENT

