pigmentation, and by BMI. In addition, we will evaluate effect modification by age and gender, as well as by sunlight exposure, calcium and phosphorus intakes from the FFQ (as these nutrients affect vitamin D bioavailability⁷⁹), and baseline risk factors for cancer and CVD. The latter interaction effects will be interpreted cautiously, as hypothesis generating. We will also examine as a prespecified secondary analysis the association among compliers, in which participants' follow-up time will be censored when they are no longer compliant with taking at least two-thirds of their assigned active agents or placebos. Finally, we will examine whether treatment effects vary over time and duration of treatment by examining survival plots and interactions with time. We will additionally conduct analyses for the primary endpoints of cancer and cardiovascular disease excluding events occurring in Year 1, as well as in Years 1 and 2, of follow-up. There may be a latent effect on both outcomes, depending on the mechanisms by which these agents act.

We will also compare the incidence of potential side effects in the active v. placebo groups for each agent, including the incidence of kidney stones with vitamin D assignment (cf. WHI calcium-vitamin D findings⁴⁴) and the incidence of GI symptoms, skin abnormalities, and bleeding with fish oil assignment (cf. JELIS findings⁴¹).

B. POWER CALCULATIONS

To calculate power, the following assumptions were made: (1) a 2x2 factorial trial in 12,500 men aged ≥ 50 and 12,500 women aged ≥ 55 ; (2) independent and equal allocation of participants to each treatment; (3) an age distribution based on that observed at baseline in our past trials for men aged ≥ 50 and women aged ≥ 55 ; (4) age-specific event rates based on the observed rates in the first 5 years of the PHS II for men and the WHS for women; (5) trial follow-up of 5 years, with little loss to follow-up as achieved in our past trials; and (6) compliance similar to that in published trials upon which our estimated rate ratio (RR) reductions are based. The cited reductions are thus the observed effects we would see in the trial. The corresponding 'true' RR is given assuming an average compliance of 80%. Power is given for a two-sided test using a logrank analysis⁸⁰ with a significance level of 0.05.

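### Does calling the 3-SD interim rule more conservative than O'Brien-Fleming, without qualification, call for a change?

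*Combined protocol and SAP*

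**What the plan says.** The interim rule is in section IX.A (Safety Monitoring) of the final protocol. On frequency: "The DSMB will annually examine the progress of the trial and the unblinded data on study endpoints". On the threshold: "interim results are compared to a z-score of 3 standard deviations", given as p=0.0027 and applied throughout the trial. On the consequence for the final test: "The final results may then be interpreted as having close to nominal significance levels". The rule is then justified: "This rule appropriately requires very strong evidence for early stopping, is more conservative than the Pocock" and O'Brien-Fleming "rules and the alpha-spending function". Nothing limits that ranking to particular looks or to total alpha.

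The same section restricts the role of the rule: "the monitoring rules will serve solely as guidelines in decisions regarding continuation or stopping of treatment arms". It adds that decisions rest on all the evidence, including other trials.

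Two other places supply inputs. Section VI.B (Power Calculations) of the final SAP fixes the test: "Power is given for a two-sided test using a logrank analysis" at the 0.05 level, with 5 years of follow-up. Section V.A (Blood Collection) of the final protocol gives expected events: "we would expect to accrue approximately 1660 cancer cases and 990 CVD cases".

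**The concern.** A flat bound and an O'Brien-Fleming bound have different shapes. O'Brien-Fleming starts very high and falls as information accrues, so a constant 3 lies below it at first and above it later. An unqualified ranking of one over the other cannot hold at every look.

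The worry is about early crossings. Someone relying on the sentence could take a 3-SD result at the first annual look as stronger evidence than an O'Brien-Fleming crossing at that look, when it is weaker. Early crossings are also the ones this trial has most reason to doubt: the run-in section expects effects on cancer prevention to be chronic, and the analysis section plans analyses that leave out events in Year 1 and in Years 1 and 2. Annual looks with staggered entry make low-information looks likely. A related question is whether a final test at 0.05, with no allowance for the looks, really keeps the error near 5%.

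**Working it through.** **Inputs.** Interim bound 3, p=0.0027, annual looks (final protocol, IX.A). Two-sided 0.05 and 5 years of follow-up (final SAP, VI.B). 1660 cancers and 990 CVD cases (final protocol, V.A). The number and spacing of looks are not stated; I assume K equally spaced looks, K = 2 to 7, with K = 5 as base case.

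**The plan's own figure.** 2 × (1 − Φ(3)) = 0.0027, as stated.

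**Bounds.** The O'Brien-Fleming bound at information fraction t is c/√t, with c found by recursive numerical integration so that the two-sided error is 0.05. It equals 3 at t = (c/3)².

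| K | c | t where the bound is 3 |
|---|---|---|
| 2 | 1.977 | 0.434 |
| 3 | 2.004 | 0.446 |
| 4 | 2.024 | 0.455 |
| 5 | 2.040 | 0.462 |
| 6 | 2.053 | 0.468 |
| 7 | 2.063 | 0.473 |

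So the rules cross at 43% to 47% of information. With three or more equal looks, at least the first interim comes before that point; with two, the only interim (50%) comes after it. For O'Brien-Fleming-type spending the answer depends on the form: a first look meets 3 at t = 0.427 if 0.05 is spent two-sided, and at 0.489 if 0.025 is spent per side. The Pocock constants for K = 2 to 7 are 2.18 to 2.49, all below 3, so the Pocock part of the sentence is right at every look.

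**Chance of crossing under the null, K = 5, cumulative, two-sided.**

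| Through look | 3 SD | O'Brien-Fleming |
|---|---|---|
| 1 | 0.27% | 0.0005% |
| 2 | 0.49% | 0.13% |
| 3 | 0.67% | 0.89% |
| 4 | 0.83% | 2.56% |

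The flat rule spends more through the second look and less from the third onward.

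**Hazard ratio at the bound.** With equal allocation, HR = exp(−2z/√d), where d is the number of events.

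- 20%, cancer, d = 0.2 × 1660 = 332: exp(−6/18.22) = 0.72 for 3 SD; exp(−9.12/18.22) = 0.61 for O'Brien-Fleming.
- 20%, CVD, d = 0.2 × 990 = 198: 0.65 against 0.52.
- 40%, d = 664 and 396: cancer 0.79 against 0.78; CVD 0.74 against 0.72.
- 60%, d = 996 and 594: cancer 0.83 against 0.85; CVD 0.78 against 0.81. The order has reversed.

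**Overall error** with 3 at each interim and 1.96 at the end: 5.08%, 5.17%, 5.25%, 5.33%, 5.40% and 5.47% for K = 2 to 7.

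**Cost of an exact 5%.** The final critical value would be 1.990 for K = 5. Using Φ(Φ⁻¹(power) + 1.96 − 1.990), power for total cancer at RR 0.85 would go from 92.7% to 92.3%, and for major CVD at RR 0.80 from 94.8% to 94.5%.

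**The case for a change.** The strongest case for a change is that monitoring bounds are applied one look at a time, so a claim about the strength of evidence for early stopping should hold at each look. The gap at the first look is large (0.27% against 0.0005%), and if the authors meant total alpha they could have said so. Their statement about guidelines limits the harm but does not make the comparison true.

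What stands is that the sentence is inaccurate for early looks under the look-by-look reading. What does not stand is that anything in the plan should be different. The threshold would be the same under any wording, and no analysis, decision rule or result depends on the ranking. That a monitoring board with biostatistical members would misread a first-look crossing because of it is conjecture. The protocol version is dated November 30, 2017 and the intervention ended on December 31, 2017, so the early looks were already past.

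A corrected ranking would also need several qualifiers. Three SD is not stricter than linear or Pocock-type spending at a first look below about 5.4% or 3.2% of information, and at the final test 1.96 is again less strict than O'Brien-Fleming (2.04 for five looks).

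Stating the number and timing of looks would be useful detail, but the flat rule does not need it to operate. Moving the final test to 1.99 is a preference, since the plan claims only approximate control and the computed error bears that out.

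**Conclusion.** No change is needed. The ranking is right against Pocock at every equally spaced look, right for total interim alpha (0.83% against 2.56% with five looks), and right at interims after about half the information. It is wrong look by look before roughly 43% to 47% of information for classical O'Brien-Fleming with two to seven equal looks, or about 43% to 49% at a first look under O'Brien-Fleming-type spending. These figures rest on the assumed looks.

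The fault is an imprecise sentence of justification. The operating rule, its p-value and the statement about the final significance level (overall error about 5.1% to 5.5%) are all correct. If the text were being edited for other reasons, a clause noting that the rule is less strict than O'Brien-Fleming at early looks would be accurate, but it would alter no conduct, analysis or conclusion.

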- Recruitment via local health fairs was added as a recruitment strategy
- Added kidney failure or dialysis, parathyroid disease, cirrhosis or severe liver disease, use of anticoagulants as additional safety exclusions
- Added that staff will contact willing participants to schedule a home visit or clinic visit for collection of blood sample
- Specified that blood assays would be performed at Quest Diagnostics (other labs were deleted)
- Revised power calculations based on lowering the eligibility age range on 6/8/11.

January 6, 2012 (v. 7)

- Add “burping” as a side effect of fish oil
- Removed atrial fibrillation as a side effect of fish oil due to inconsistent evidence.

December 3, 2012 (v. 8)

- Specified that study will be conducted among 25,000 men and women
- Specified that the mailing company will conduct recruitment mailings in volume of 0.5-1 million per drop

- The number of willing and eligible persons to receive screening questionnaire (V-2) was projected to be 160,000
- Specified that non-responders to run-in follow-up questionnaire (V-3) will receive up to 3 requests for data
- Specified that toward the end of the enrollment phase, as a mechanism to enhance minority representation in the trial, we will impose a stricter compliance standard on white, non-Hispanic enrollees who live outside the 60-mile range for CTSC recruitment: not eligible if a blood sample is not returned and missed more than 5 days of run-in placebo pills in past month
- Contacting the “not sure” and “no” respondents to question about providing a blood sample to inform them that we can arrange a home visit if they wanted
- Study guidelines amended to encourage randomized participants to inform their physicians about their participation in the trial if they receive a post-randomization diagnosis of hypercalcemia, sarcoidosis, or other safety issues
- Provided new power calculations based upon a study population of 25,000

April 1, 2013 (v. 9)

- Blood sample analyses now to include measures of biomarkers related to CVD (cholesterol lipoprotein sub-fractions) – to be conducted at Atherotech Diagnostic Labs
- Specified that non-responders to annual follow-up questionnaires will receive up to 5 requests for information

September 10, 2013 (v. 10)

- Added information about the SELECT Study results (observational association between omega-3 fatty acids and risk of prostate cancer) to the “Background and Significance” section of protocol

September 17, 2013 (v. 11)

- Specified that the projected randomized population would be a maximum of 26,500
- Added biochemical assays of blood specimens of metabolomic/lipidomic biomarkers for baseline and follow-up samples

December 5, 2013 (v. 12)

- Specified that internet sources will be used to assist in the tracking (i.e., search for new address and phone numbers) of participants potentially lost to follow-up

December 17, 2013 (v. 13)

- Added measurement of plasma levels of PCSK9 and plasma-based genotypes for PCSK9

March 19, 2014 (v. 14)

- Specified an increase in the target for optional follow-up blood sample from 2,000 to 6,000. Deletion of “random” to describe selection of follow-up samples, as participants asked to provide the samples will be those scheduled for an ancillary blood draw at a home visit.

May 21, 2014 (v. 15)

- Specified that participants will be given the option of completing their annual questionnaire via the Internet.

June 19, 2014 (v. 16)

- Specified the planned collection of the follow-up Diet Assessment at 3 years instead of 2 years
- Added as a tertiary aim whether vitamin D or omega-3 supplementation reduces the risks of heart failure (ancillary study)

November 11, 2015 (v. 17)

- Specified that the follow-up Diet Assessment would be conducted at 4.5 years instead of 3 years
- Added to “Endpoint Ascertainment” section: Additional endpoints of interest include heart failure, colorectal polyps, and periodontal disease.

January 6, 2016 (v. 18)

- Added biochemical assays: measures of metabolomics and lipidomic biomarkers to be done at LabCorp in addition to the metabolomics laboratory at UCSD

April 29, 2016 (v. 19)

- Deleted reference to an additional Diet Assessment at conclusion of the trial (to minimize participant burden).

September 12, 2016 (v. 20)

- To increase completeness of ascertainment of study outcome data (for MI, stroke, revascularization, and cancer), specified that Medicare/CMS linkage would be done. However, participants will be directly asked to provide authorization to obtain medical records to validate outcomes ascertained from Medicare/CMS.

January 27, 2017 (v. 21)

- Specified the addition of biochemical assays: albumin, creatinine, liver function, lipid tests, cholesterol efflux, epigenetic biomarkers.

September 13, 2017 (v. 22)

- Specified that, at the conclusion of the randomized trial, we will send participants two additional annual questionnaires to collect supplemental study data during the post-intervention phase.

November 30, 2017 (v. 23) is the current protocol. A copy is provided.

- Clarified that we will additionally conduct analyses excluding events occurring in year 1 and years 1-2 of follow-up (our original protocol on 1/28/10 [v.2] specified: “Finally, we will examine whether treatment effects vary over time and duration of treatment by examining survival plots and interactions with time. There may be a latent effect on cancer incidence, depending on the stage of carcinogenesis during which these agents act.” In the 11/30/17 protocol, we formalized this as analyses excluding events during year 1 and years 1-2 of follow-up.)
- Data analysis section amplified: specified sensitivity analyses by compliance, with participants’ follow-up time censored when they are no longer compliant with taking at least two-thirds of their assigned active agents or placebos (as in our previous trials).

NOTE: VITAL investigators were unblinded to randomization treatment codes on December 6, 2017 prior to a teleconference with VITAL DSMB members. All of the above protocol changes were made PRIOR to the investigator unblinding on December 6, 2017. The intervention phase of VITAL ended on December 31, 2017.

VI. BIostatistical Analysis**A. Data Analysis**

Analyses of treatment effects will be based on the intent-to-treat principle. The first analysis will compare baseline characteristics by randomized treatment assignment to ensure that balance was achieved by the randomization. Characteristics to be examined include known risk factors for cancer and CVD, including age; gender; race/ethnicity; BMI; smoking; alcohol use; physical activity; medical conditions such as hypertension, hyperlipidemia, diabetes, and family history of cancer and CVD; and baseline vitamin D and omega-3 fatty acid levels as assessed by dietary questionnaire in all participants and blood assays in a case-cohort subsample. The large sample size, as well as successful balance of known potential confounders, will provide assurance that unmeasured or unknown potential confounders will also be equally distributed across randomized treatment groups.

In this 2x2 factorial design, the primary aim is to compare the main effects of intention-to-treat with vitamin D and with fish oil on cancer and CVD. We will use the Cox proportional hazards model to allow for variable follow-up lengths⁷⁶ and will estimate the hazard ratio for each intervention using indicators for treatment exposure, controlling for the second intervention, age, and gender. Because the cohort will consist of older individuals, competing risks due to deaths from other causes will be considered. The primary analysis will estimate the cause-specific hazard and the hazard ratio comparing intervention groups for each outcome of interest by censoring individuals with deaths due to competing causes. To estimate the cumulative incidence function, the subdistribution of each endpoint will be plotted over time.^{77, 78} The alternative Fine and Gray approach⁷⁹ models the effect of treatment on the subdistribution hazard or directly on the cumulative incidence function. While we will consider this and compare its fit to the model-free cumulative incidence curves,⁷⁸ the proportional hazards approach will be our primary analysis.

Similar analyses will be conducted for both cancer and CVD. For cancer, we will estimate the intervention effects on the primary endpoint of total cancer, as well as the secondary outcomes of breast, prostate, and colorectal cancer, and cancer mortality. For CVD we will estimate the effects on the primary composite endpoint of major CVD (MI, stroke, and cardiovascular mortality); on the secondary composite endpoint that additionally includes coronary revascularization; and on the individual components of MI, stroke, revascularization, and cardiovascular mortality.

Beyond the primary analyses, we will examine effect modification by the other randomized intervention, by baseline risk factors, and by time. We have a particular interest in exploring interactions between the interventions, as well as with the baseline plasma biomarkers of 25(OH)D for vitamin D and of EPA+DHA for fish oil. We hypothesize that the intervention effects may be larger among those with below-median baseline levels, and will examine treatment effects by quartiles of these biomarkers. The biomarker data will be analyzed as a case-cohort study using methods for proportional hazards regression.⁸⁰ Because of the frequency matching by age and gender, appropriate stratum-specific weighting of the observations will be employed.⁸¹ We also have a prior interest in the effects of the vitamin D intervention within

groups defined by race/ethnicity and skin pigmentation, and by BMI. In addition, we will evaluate effect modification by age and gender, as well as by sunlight exposure, calcium and phosphorus intakes from the FFQ (as these nutrients affect vitamin D bioavailability⁸²), and baseline risk factors for cancer and CVD. The latter interaction effects will be interpreted cautiously, as hypothesis generating. Finally, we will examine whether treatment effects vary over time and duration of treatment by examining survival plots and interactions with time. There may be a latent effect on cancer incidence, depending on the stage of carcinogenesis during which these agents act.

We will also compare the incidence of potential side effects in the active v. placebo groups for each agent, including the incidence of kidney stones with vitamin D assignment (cf. WHI calcium-vitamin D findings⁴⁴) and the incidence of GI symptoms, skin abnormalities, and bleeding with fish oil assignment (cf. JELIS findings⁴¹).

B. POWER CALCULATIONS

To calculate power, the following assumptions were made: (1) a 2x2 factorial trial in 10,000 men aged ≥ 60 and 10,000 women aged ≥ 65 ; (2) independent and equal allocation of participants to each treatment; (3) an age distribution based on that observed at baseline in our past trials for men aged ≥ 60 and women aged ≥ 65 ; (4) age-specific event rates based on the observed rates in the first 5 years of the PHS II for men and the WHS for women; (5) trial follow-up of 5 years, with little loss to follow-up as achieved in our past trials; and (6) compliance similar to that in published trials upon which our estimated rate ratio (RR) reductions are based. The cited reductions are thus the observed effects we would see in the trial. The corresponding ‘true’ RR is given assuming an average compliance of 80%. Power is given for a two-sided test using a logrank analysis⁸³ with a significance level of 0.05.

Cancer: Assuming that only one agent is effective, with 5 years of treatment and follow-up we will have 91% power to detect an observed RR of 0.85 for the primary endpoint of total cancer incidence (Table 1). For prostate cancer, we will have 88% power

Observed RR†	True RR	Total Cancer	Cancer Mortality	Colorectal Cancer	Breast Cancer (Women)	Prostate Cancer (Men)
0.90	0.875	58.7	-	-	-	-
0.85	0.812	91.1	-	-	-	-
0.80	0.750	99.4	52.0	31.8	34.6	70.1
0.75	0.687	>99.9	72.2	47.0	50.9	88.3
0.70	0.625	>99.9	87.3	63.1	67.5	96.9
0.65	0.560	>99.9	95.6	77.6	81.5	99.5
0.60	0.500	>99.9	98.9	88.4	91.2	>99.9

†Observed RR=intent-to-treat RR, including noncompliant participants. Compliance assumed to be 80%. True RR=that with perfect compliance.

to detect a 25% risk reduction. For breast cancer, we will have 81% power to detect a 35% risk reduction. For colorectal cancer, we will have 78% power to detect a 35% risk reduction and 88% power to detect a 40% risk reduction. For cancer mortality, we will have 87% power to detect a 30% risk reduction. If both agents are effective in preventing cancer but act independently, power would be reduced slightly due to a somewhat smaller overall number of events. If the agents interact, however, power will be affected to the extent of the interaction. Should the agents act synergistically, power would increase, as illustrated in Table 2 for the outcome of total cancer.

For example, if the effect of each agent alone is a reduction of 10%, but in combination the effect is stronger, with an additional 10% decrease, the RR comparing the combined group to the all placebo group would be 0.73, versus 0.81 with additive effects (on the multiplicative

scale). Power for the main effect of each agent would then increase to 86% (or higher with greater synergy). The trial would have power to detect moderate-to-large interactions, as shown in Table 2. Should the agents interact in a subadditive fashion, power would be reduced to the extent of the subadditivity. Power to explore effect modification by baseline blood levels of 25(OH)D and EPA+DHA among those above and below the median level in the cohort will be lower because we anticipate that about 60% of participants will provide blood specimens. We will have about 90% power to detect an interaction of size 0.6.

Power has been shown for a given observed reduction in risk, assuming compliance similar to that seen in current randomized trials such as the WHS and PHS. For total cancer, our power will be excellent with a 5-year follow-up even if compliance is lower. For example, if the true reduction in risk is 20%, the observed RR corresponding to compliance of 80% is 84%, and we have 94% power to detect this level of effect. If compliance is only 75%, the observed RR would be 0.85, for which we would have 91% power. Finally, if compliance is only 70%, the observed RR would be 0.86, and we would still have 87% power to detect an effect of this magnitude.

Table 2. Power for interaction effects on total cancer in a factorial trial of 10,000 men aged ≥60 and 10,000 women aged ≥65 with 5 years of follow-up				
RR	Interaction†	RR	Power	
Single agent†		Both agents	Main Effect	Interaction
0.90	1.0	0.81	56.3	
	0.9	0.73	86.3	
	0.8	0.65	98.0	57.9
	0.7	0.57	99.9	92.1
0.85	1.0	0.72	88.7	
	0.9	0.65	98.1	
	0.8	0.58	99.8	55.0
	0.7	0.51	>99.9	90.2
0.80	1.0	0.64	98.8	
	0.9	0.58	99.9	
	0.8	0.51	>99.9	52.0
	0.7	0.45	>99.9	87.9

†RR = intent-to-treat RR, including noncompliant participants (assuming 80% compliance). Represents the effect among those not assigned to the other intervention and assumes the same effect for both agents. The interaction is the RR for the combined group divided by the product of risks for the two separate groups—i.e., $RR_{int} = RR_{both} / (RR_{vit D alone} * RR_{fish oil alone})$. An interaction=1 implies additive effects (no interaction).

CVD: As shown in Table 3, assuming that only one agent is effective, with 5 years of treatment and follow-up we will have 92% power to detect an observed RR of 0.80 for the primary composite endpoint of MI, stroke, and cardiovascular mortality. For the secondary composite endpoint of MI, stroke, cardiovascular mortality, and coronary revascularization, we will have 99% power to detect a 20% reduction and 90% power to detect a 15% reduction. With a RR of 0.70 we will have 87% power for cardiovascular mortality, 88% power for MI, and 90% power for stroke. If both agents are effective in preventing CVD but act independently, power would be reduced only slightly due to a smaller overall number of events. If the agents act synergistically, power would increase, as described for cancer. If the agents interact in subadditive fashion, power would be reduced to the extent of the subadditivity.

Table 3. Power for effects of a single agent on CVD in a factorial trial of 10,000 men aged ≥60 and 10,000 women aged ≥65, with 5 years of follow-up

Observed RR†	True RR	Major CVD	Total CVD	CVD Mortality	MI	Stroke
0.90	0.875	38.1	57.3	-	-	-
0.85	0.812	71.1	90.2	-	-	-
0.80	0.750	92.5	99.2	51.8	53.5	56.1
0.75	0.687	99.0	>99.9	71.9	73.8	76.3
0.70	0.625	99.9	>99.9	87.1	88.5	90.3
0.65	0.560	>99.9	>99.9	95.6	96.3	97.1
0.60	0.500	>99.9	>99.9	98.9	99.1	99.4

†Observed RR=intent-to-treat RR, including noncompliant participants. Compliance is assumed to be 80%. True RR=that with perfect compliance.

For total CVD, our power would be somewhat lower—but still adequate—with more limited compliance. If the true effect is a 25% reduction, power would be 92% if compliance is 80% (observed RR=0.80), 89% if compliance is 75% (observed RR=0.813), and 84% if compliance is 70% (observed RR=0.825). To achieve 80% power for CVD, we would need an observed RR of at least 0.83, which corresponds to a true reduction of 21% under 80% compliance and 24% under 70% compliance.

IX. MONITORING AND QUALITY ASSURANCE

A. SAFETY MONITORING

An independent Data and Safety Monitoring Board (DSMB) will be assembled, consisting of experts in clinical trials, epidemiology, biostatistics, relevant clinical areas of cancer and CVD, and NIH representatives. The Physicians' Health Study, the Women's Health Study, and the Women's Antioxidant and Folic Acid Cardiovascular Study have been monitored by the same DSMB since their inception. As two of these trials have ended and the third is in its last years, we will ask our DSMB members if they would be willing to also monitor VITAL. If they are not able to do so, we will consult with them in assembling a new DSMB.

The DSMB will annually examine the progress of the trial and the unblinded data on study endpoints and possible adverse effects to recommend continuation, alteration of study design, or early termination, as appropriate. Interim trial results will be assessed with the Haybittle-Peto rule,^{84, 85} adjusting for multiple looks. In this method, interim results are compared to a z-score of 3 standard deviations ($p=0.0027$) throughout the trial. The final results may then be interpreted as having close to nominal significance levels. This rule appropriately requires very strong evidence for early stopping, is more conservative than the Pocock⁸⁶ and O'Brien-Fleming⁸⁷ rules and the alpha-spending function,⁸⁸ and can be conducted at convenient times without inducing statistical complexity.⁸⁹

While these rules are intended for the primary endpoints, the goal of VITAL is to assess the overall balance of benefits and risks of the two agents in the primary prevention of cancer and CVD. Thus, consideration will also be given to the secondary endpoints that are needed in the interpretation of overall results. In addition, the monitoring rules will serve solely as guidelines in

decisions regarding continuation or stopping of treatment arms. All decisions must be made after examining the totality of evidence, including other trial data, on these agents.

X. REFERENCES

2. Institute of Medicine Food and Nutrition Board. Dietary Reference Intakes: Calcium, Phosphorous, Magnesium, Vitamin D and Fluoride. Washington DC: National Academies Press, 1999.
